## 6.9 Adverse Event Assessments

Information regarding the occurrence of AEs will be collected from the time the subject signs the informed consent form and continuing through the last study visit. Findings at screening and Day 0 (pre-dose) will be recorded as medical history. Any known untoward event that occurs beyond the AE reporting period that the Investigator assesses as related to study drug also should be reported as an AE. Clinical AEs will be graded using the NCI CTCAE, Version 4.03 ([Appendix 1](#)).

**Note:** AEs resulting in a subject's permanent discontinuation from the study, regardless of seriousness or relationship to study drug, MUST be promptly reported to the sponsor. Additionally, subjects must be followed until return to normal and/or resolution of the AE.

See [Section 10](#) for more information.

## 6.10 Prior and Concomitant Medications

All WAIHA treatments and all other treatments a subject receives within at least 3 months prior to screening through the end of study will be documented.

In cases in which concomitant medications are used, details to be recorded include the following: medication name, start date and time, stop date and time, dose, route, frequency, and reason for use. The concomitant medication names are to be coded using the World Health Organization (WHO) Drug Dictionary (WHO-DD March 2013, Type B2 or later) and classified by anatomical therapeutic chemical (ATC) categories.

### **Permitted Medications**

The following concomitant medications and treatment for co-existing conditions, including those for WAIHA, are permitted if not listed as prohibited:

1. Concomitant treatment that is medically indicated for any AEs the subject experiences during the study.
2. Medication for potential infusion-related reactions (IRRs), including post-infusion headache: The Investigator may recommend prophylactic use of acetaminophen, IV hydration, diphenhydramine, or histamine2 blockers (eg, ranitidine, famotidine).
3. Stable regimen of the following systemic immunosuppressants: azathioprine, mycophenolate mofetil, low-dose methotrexate, cyclosporine, tacrolimus, sirolimus, corticosteroids, or low-dose oral cyclophosphamide ( $\leq 100$  mg/day).

### **Prohibited Medications**

The following treatments are prohibited during the study unless specified above as permitted:

1. Rituximab or other anti-CD20 antibody
2. Monoclonal antibodies other than study drug.
3. Any immunosuppressive drugs apart from those that are listed as permitted.
4. Any cytotoxic agent other than azathioprine, chlorambucil, low-dose methotrexate, or low-dose oral cyclophosphamide ( $\leq 100$  mg/day).
5. IV corticosteroids prior to infusion of study drug (except in subjects who received corticosteroids for treatment of a prior infusion reaction to SYNT001).
6. Any investigational drug or device.
7. Vaccinations within 2 weeks of screening through 28 days following final dose of study drug.

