#### **From screening until 2 weeks after the last dose of SYNT001**

The dose of corticosteroids taken for WAIHA or any other condition should remain stable ( $< 10\%$  change in dose level) from screening until 2 weeks after the last dose of SYNT001.

Corticosteroids should neither be started nor discontinued during this period with the exception of subjects who experience an IRR that requires corticosteroids as part of the management of the

IRR. Such subjects may receive corticosteroids prophylactically prior to subsequent SYNT001 infusions at the discretion of the Investigator.

From 2 weeks after the last dose of SYNT001 until end of study participation

At the discretion of the Investigator, but only after at least 2 weeks beyond the last dose of SYNT001, a slow corticosteroid taper may be started as per the following suggested schedule:

- If on >30 mg of prednisone per day, decrease by no more than 10 mg every two weeks until a final dose.

If per the Investigator's judgement, the subject would benefit from a change to the WAIHA treatment beyond the allowed steroid taper, this will be considered on a case-by-case basis in consultation with the Sponsor.

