## **8. STUDY RULES**

### **8.1 Subject Withdrawal**

Every reasonable effort will be made to keep the subject in the study; however, if a subject withdraws from the study, the Investigator should complete and report the reasons for withdrawal as thoroughly as possible. The reason(s) for termination must be clearly documented on the appropriate page of the eCRF.

Subjects who have received at least one SYNT001 dose and withdraws or prematurely discontinue study drug should be encouraged to attend, at a minimum, the early termination (ET) visit (Day 112 for Cohort 1 or Day 91 for Cohort 2). Subjects in Cohort 2 will also be encouraged to attend the remaining follow up visits on Days 112, and 140.

If the subject fails to return for these assessments for unknown reasons, every effort (eg, telephone, email, and letter) should be made to contact them.

A subject's participation in the study may be prematurely discontinued for any of the following reasons:

1. The subject wishes to withdraw from the study.
2. Request by a regulatory agency or IRB.
3. Subject experiences a significant or intolerable AE.
4. The subject experiences a significant adverse change in vital signs, physical examination findings, or clinical laboratory parameter.
5. The subject has a need for a concomitant medication that is not permitted by the study protocol.
6. The subject experiences generalized impairment or mental incompetence that would result in the subject being unable to understand his or her participation in the study.
7. If, in the Investigator's medical judgment, further participation would be injurious to the health and well-being of the subject or is not in the best interest of the subject.
8. Administrative reasons, such as subject non-compliance or a major protocol violation.

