### 8.5.3 Individual Stopping Rule

Dosing for any individual subject will be discontinued (ie, further treatment with the study drug will not be given) if the subject experiences any study drug-related SAE or any study drug-related non-serious AE that, in the judgement of the Investigator (following consultation with Medical Monitor, if desired) suggests that it could be unsafe to administer further study drug to that subject.

Subjects who withdraw from this study due to an AE determined to be related to study drug are to be followed until there is:

- Resolution or stabilization of the AE determined to be related
- The subject is lost to follow-up
- The event is otherwise explained

If there is a persistent AE contributing to discontinuation that is determined to be related to SYNT001, subjects must be followed with appropriate medical management until resolution or stabilization.

Additionally, a subject will be discontinued from further treatment with study drug, at the discretion of the Investigator with consultation with the Medical Monitor, if they require a significant increase in doses of anti-WAIHA medications for the management of WAIHA.

If dosing with study drug is stopped because of an AE/SAE, or because of significant increase in doses of anti-WAIHA medications, or any other reason for prematurely discontinuation of study drug during the treatment period, the subject should be encouraged to attend, at a minimum, the ET visit (Day 112 for Cohort 1 or Day 91 for Cohort 2). Subjects in Cohort 2 will also be encouraged to attend the remaining follow up visits on Days 112, and 140.

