### **10.2 Adverse Event Definition**

An AE is defined as any untoward medical occurrence in a clinical trial subject associated with the use of a drug, whether considered drug related. An AE can be an unfavorable and unintended sign (eg, an abnormal laboratory value finding), a symptom, or a disease temporally associated with the use of a drug, without judgment as to causality. An AE can arise from use of the drug (eg, use in combination with another drug) and from any route of administration, formulation or dose, including an overdose. An AE also includes, but is not limited to, any clinically significant worsening of a pre-existing condition. Examples include:

- Any sign, symptom, physical finding, or laboratory result that has worsened in nature, severity or frequency compared to baseline;
- Reactions from an investigational drug, including those occurring because of an overdose, abuse of the study drug, withdrawal phenomena, sensitivity or toxicity;
- Concurrent illness that was not present or worsens in nature, severity, or frequency compared to baseline;
- Injury or accident; and/or
- Exacerbation of a pre-existing condition.

For data collection, all untoward events that occur after informed consent through the last study visit are to be recorded on eCRFs by the investigational site.

While pregnancy alone is not considered as an AE or SAE, any pregnancy complication(s) should be recorded as an AE(s) or SAE(s) (if applicable). Elective abortions without complications should not be regarded as AEs, unless they were therapeutic abortions (see below). Hospitalization for normal delivery of a healthy newborn should not be considered an SAE. If a female subject becomes pregnant during the conduct of the study, the Investigator must notify the Sponsor according to the procedures provided in [Section 10.3.8](#)).

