### 11.2 Sample Size Justification

Formal sample size calculations were not performed. The number of subjects was chosen based on feasibility and was considered sufficient to meet the study objectives.

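### Protocol 6.10 can be read both to permit and to bar a corticosteroid start or increase for a hemolytic flare, and the SAP pools the disease-marker values that follow

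*Protocol*

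**What the plan says.** **The two lists.** In Protocol 6.10, Permitted Medications, concomitant treatments (WAIHA treatments included) "are permitted if not listed as prohibited". Item 1 of that list is "Concomitant treatment that is medically indicated for any AEs the subject experiences during the study". Prohibited Medications begins: "The following treatments are prohibited during the study unless specified above as permitted". The synopsis uses equivalent wording. No order of precedence is given.

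**The adverse event definition.** Protocol 10.2 includes clinically significant worsening of a pre-existing condition and gives as an example "Exacerbation of a pre-existing condition". It makes no exception for the disease under study.

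**The lock.** From screening to two weeks past the final SYNT001 dose, corticosteroid dose should change by less than 10%, and "Corticosteroids should neither be started nor discontinued during this period with the exception of subjects who experience an IRR" that needs corticosteroids for its management. Under WAIHA Co-medication, subjects on WAIHA treatment at enrollment should keep a stable regimen during dosing and for 14 days after.

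**Leaving treatment or the study.** Section 8.1 lists reasons for which participation may be ended early. The fifth is "The subject has a need for a concomitant medication that is not permitted by the study protocol". Section 8.5.3 has study drug stopped, at the Investigator's discretion in consultation with the Medical Monitor, "if they require a significant increase in doses of anti-WAIHA medications for the management of WAIHA".

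**The analysis.** SAP 4.8.2 summarizes disease-marker values and their changes from baseline by cohort. SAP 4.9.3 tabulates corticosteroid use and dose by cohort and visit. Neither section links one to the other.

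**The concern.** A site treating a hemolytic flare during dosing can find support in 6.10 for starting or raising a corticosteroid, because the flare is an adverse event. It can also find a rule in 6.10 against doing so, because the flare is not an IRR. Section 8.5.3 assumes that an increase can happen, and does not say when SYNT001 must stop.

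Two things follow. Sites may classify the same event differently: as permitted treatment, or as a deviation that may appear in the SAP 4.4 deviation table. And hemoglobin, LDH, haptoglobin and bilirubin are secondary endpoints in an open-label study without a control arm, so a recovery produced by rescue can be read as a SYNT001 effect. Corticosteroid use is itself an exploratory endpoint, and its meaning depends on the same rule.

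**Working it through.** There is no design figure to reproduce: "Formal sample size calculations were not performed" (Protocol 11.2). The check sets the clauses side by side for one case: an oral corticosteroid started, or raised by 10% or more, for a hemolytic flare during dosing.

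| Clause | Bearing on the case | Points to |
|---|---|---|
| 10.2 | Exacerbation of an existing condition is an adverse event | Flare is an adverse event |
| 6.10 permitted item 1 | Treatment for any adverse event, no limit by drug or cause | Permitted |
| 6.10 permitted item 3 | Corticosteroids named, as part of a stable regimen | Silent, or against |
| 6.10 prohibited item 3 | Immunosuppressants not listed as permitted | Unclear; yields to the permitted list |
| 6.10 prohibited item 5 | IV corticosteroids before infusion | Does not reach an oral drug |
| 6.10 Corticosteroids | No start, change below 10%, IRR the only exception | Barred |
| 6.10 WAIHA Co-medication | Stable regimen if on WAIHA treatment at enrollment | Barred for those subjects |
| 8.1 reason 5 | Participation may end if the drug is not permitted | Depends on the answer sought |
| 8.5.3 | SYNT001 stopped at discretion after a significant increase, undefined | Assumes that an increase occurs |

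Section 8.5.3 does not settle the matter. The lock runs two weeks beyond the final dose, so stopping SYNT001 does not by itself release the increase. The case-by-case route for other WAIHA treatment changes is written under the period that begins after the lock ends.

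**Reach of the lock** (nominal days, from the visit schedules and Protocol Table 7):

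- Cohort 1: last dose Day 28, so the lock ends on Day 28 + 14 = Day 42. Post-baseline hemoglobin is scheduled on Days 7, 14, 21, 28, 33, 42, 56, 84 and 112. Six of 9 fall inside.
- Cohort 2, every-other-week maintenance: last dose Day 84, so the lock ends on Day 84 + 14 = Day 98. Hemoglobin is scheduled on Days 7, 14, 28, 42, 56, 70, 84, 91 and 140. Eight of 9 fall inside.

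**Illustration of the effect on a mean.** Assume that k of n subjects are rescued and that each gains d g/dL of hemoglobin from rescue. The cohort mean change then moves by k × d / n. The values of k and d are assumptions; n is the maximum cohort size.

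| Cohort | k | d = 1 g/dL | d = 3 g/dL |
|---|---|---|---|
| 1 (n = 8) | 1 | 1 × 1/8 = 0.13 | 1 × 3/8 = 0.38 |
| 1 (n = 8) | 2 | 2 × 1/8 = 0.25 | 2 × 3/8 = 0.75 |
| 2 (n = 12) | 1 | 1 × 1/12 = 0.08 | 1 × 3/12 = 0.25 |
| 2 (n = 12) | 2 | 2 × 1/12 = 0.17 | 2 × 3/12 = 0.50 |

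**Stopping study drug does not remove these values.** Subjects who stop early are encouraged to attend later visits (Protocol 8.1, 8.5.3), and the PD population is everyone dosed who has post-dose PD data (SAP 4.2).

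**The case against.** The best defense is that a specific rule governs a general one. The corticosteroid rule covers WAIHA or any other condition and names its one exception. Permitted item 3 allows corticosteroids only as part of a stable regimen. Section 8.5.3 lists an adverse event and an increase in anti-WAIHA drugs as separate reasons for stopping, which suggests that WAIHA escalation was meant to follow its own rule. This is a reasonable reading, but the protocol does not state it. The one exception is itself an adverse event, hemolysis is not mentioned, and no clause is ranked above another.

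A reader might also infer more than the documents support:

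- **That the adverse-event permission overrides the prohibited list, so anti-CD20 antibody is allowed for a flare.** The permitted list yields to the prohibited list as well, and anti-CD20 antibody is named there. For named drugs the text is circular, and neither list wins.
- **That all rescue for hemolysis is both allowed and forbidden.** Transfusion is not prohibited, and red-cell units are counted as an exploratory endpoint.
- **That the subject necessarily stays on SYNT001.** Section 8.5.3 gives a route to stop, though a discretionary one.
- **That Sections 8.1 and 8.5.3 contradict each other.** One concerns participation in the study and the other study drug, so both can apply.

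Two further objections stand. Protocol 6.10 already records start and stop dates, dose and reason for use, so values after rescue can be identified without a new form. And the disease markers are descriptive secondary endpoints with no hypothesis test; the primary endpoint is safety.

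**Conclusion.** The conflict is in the text, in a narrow form. The two lists are circular, and the permission to treat any adverse event collides with a corticosteroid and co-medication lock whose only exception is an IRR. A corticosteroid start or increase for a flare can be read as permitted or as a deviation, with SYNT001 continued or stopped.

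The window concerned covers 6 of 9 (Cohort 1) and 8 of 9 (Cohort 2) scheduled post-baseline hemoglobin visits by nominal day, and SAP 4.8.2 has no rule for values after rescue. How far this would move the summaries cannot be estimated from the documents. The illustrated shifts of 0.08 to 0.75 g/dL rest wholly on assumed numbers of rescued subjects and assumed gains, at full cohort size. The repair is worth making because it is cheap and affects how sites handle and classify a foreseeable event. The point does not invalidate the design.

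**What to change.** **Protocol.** Reconcile the synopsis text on concomitant treatment with Sections 6.10 (both list lead-ins, permitted item 1, WAIHA Co-medication and Corticosteroids), 8.1, 8.5.3 and 10.2. They should agree on how drug treatment for worsening WAIHA in the locked period is classified. State which list governs when both apply, and whether permitted item 1 covers a WAIHA exacerbation. Which clinical rule is right is for the sponsor and investigators to decide; this review takes no position.

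**SAP 4.8.2.** Using the concomitant-medication dates, doses and reasons already collected, identify every disease-marker value that follows a start or increase of WAIHA therapy, and mark those values in the summaries, so that a rescue effect is not read as a SYNT001 effect.

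**Cost.** Amended protocol wording, a short SAP addition before database lock, and some programming. No extra visits or samples are needed, and no new eCRF flag is essential.

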### **WAIHA Co-medication**

Subjects receiving WAIHA treatment at enrollment, should remain on a stable treatment regimen throughout dosing and for the 14 days after the last dose of SYNT001.

### **Corticosteroids**

#### **Before enrollment**

The dose of corticosteroids taken for WAIHA or any other condition prior to screening must be at a dose  $\leq 1$  mg/kg and the dose level must have not increased in dose level by more than 50% in the 2 weeks prior to screening. No pulse dosing of steroids is permitted in the 2 weeks prior to screening.

#### **From screening until 2 weeks after the last dose of SYNT001**

The dose of corticosteroids taken for WAIHA or any other condition should remain stable ( $< 10\%$  change in dose level) from screening until 2 weeks after the last dose of SYNT001.

Corticosteroids should neither be started nor discontinued during this period with the exception of subjects who experience an IRR that requires corticosteroids as part of the management of the

IRR. Such subjects may receive corticosteroids prophylactically prior to subsequent SYNT001 infusions at the discretion of the Investigator.

From 2 weeks after the last dose of SYNT001 until end of study participation

At the discretion of the Investigator, but only after at least 2 weeks beyond the last dose of SYNT001, a slow corticosteroid taper may be started as per the following suggested schedule:

- If on >30 mg of prednisone per day, decrease by no more than 10 mg every two weeks until a final dose.

If per the Investigator's judgement, the subject would benefit from a change to the WAIHA treatment beyond the allowed steroid taper, this will be considered on a case-by-case basis in consultation with the Sponsor.

## 7. STUDY ASSESSMENTS

### 7.1 Cohort 1 Assessments

#### 7.1.1 Screening Period: Day –14 to Day –1

Informed consent must be obtained before any study-specific samples are taken or study-specific tests or evaluations are conducted. The following assessments at the screening visit are to occur within 14 days before dosing. Study eligibility will be based on satisfying all the study inclusion and exclusion criteria.

At the screening visit, information will be collected and subjects will have clinical evaluations as follows:

- Informed consent ([Section 6.1](#))
- Medical history and demographic data ([Section 6.2](#))
- Review inclusion and exclusion criteria ([Section 5.2](#), [Section 5.3](#))
- Complete physical examination, including height and weight ([Section 6.3](#))
- Vital sign measurements (after 5 minutes of rest; sitting blood pressure, heart rate, respiratory rate, oral temperature); abnormal results to be repeated after 5 minutes of rest ([Section 6.5](#))
- Karnofsky Performance Scale ([Section 6.4](#))
- Clinical safety laboratory tests (hematology, serum chemistry panel, urinalysis) ([Section 6.7](#))
- Pregnancy test ([Section 6.7](#))
- Hepatitis and HIV antibody screen ([Section 6.7](#))
- 12-lead ECG (to be obtained in triplicate after 5 minutes of rest in the supine position) ([Section 6.6](#))
- PD sample collection ([Section 6.7](#))
  - IgG, IgG subtypes (IgG1-4), IgA, IgM
  - Haptoglobin
  - Direct Coombs test
- Concomitant medication assessment ([Section 6.10](#))
- AE assessment ([Section 6.9](#))

#### 7.1.2 Enrollment and First Treatment: Day 0

Study Day 0 is defined as the date the subject is administered their first dose of study drug. On Day 0, subjects will be asked to come to the clinic and the following procedures will be performed prior to the first dose of study drug:

- Complete physical examination ([Section 6.3](#))
- Vital sign measurements (sitting blood pressure, heart rate, respiratory rate, oral temperature); to be measured immediately prior to the infusion ([Section 6.5](#))
- Pulse oximetry (to be measured immediately prior to the infusion) ([Section 6.5](#))

- Clinical safety laboratory tests (hematology, serum chemistry panel, urinalysis) ([Section 6.7](#))
- Pregnancy test ([Section 6.7](#))
- Serum tetanus antibody and VZV antibody ([Section 6.7](#))
- PK baseline sample collection (collected just prior to the start of the study drug infusion) ([Section 6.7](#))
- Immunogenicity sample collection (collected just prior to the start of study drug infusion) ([Section 6.7](#))
- PD sample collection (collected just prior to the start of the study drug infusion) ([Section 6.7](#))
  - IgG, IgG subtypes (IgG1-4), IgA, IgM and CIC
  - Haptoglobin
  - Direct Coombs test
  - D-dimer
  - Antiphospholipid antibodies (lupus anticoagulant, anti-cardiolipin, and anti-beta-2-GP1 antibodies)
  - ANA and anti-dsDNA antibody titers
  - C3
  - Cold agglutinins (titer and thermal amplitude)
  - Quantitative Coombs assay
  - Exploratory biomarkers (*FCGR2A* SNP via buccal swab, RNA sequencing [RNAseq], urine IgG)
  - Immune phenotyping by flow cytometry for measurement of CD3+CD4+ T, CD3+CD8+ T, monocytes, NK cells and B cells
- Concomitant medication assessment ([Section 6.10](#))
- AE assessment ([Section 6.9](#))

**After the preceding procedures and assessments are completed:**

- Study drug administration (record date and time of dose of study drug) ([Section 9](#))
- Vital sign measurements (sitting blood pressure, heart rate, respiratory rate, oral temperature) will be performed at 15, 30, and 45 minutes after the start of the infusion and at completion of the infusion ([Section 6.5](#))
- Pulse oximetry will be measured at 15, 30, and 45 minutes after the start of the infusion and at completion of the infusion ([Section 6.5](#))
- Concomitant medication assessment ([Section 6.10](#))
- AE assessment ([Section 6.9](#))

